## 8.1 Screening

If for any reason the subject is a screen failure, the subject may be rescreened once only. If a subject rescreens for the study, **then the subject must sign a new ICF** and be issued a new subject number prior to any screening assessment being conducted for the subject under the new screening subject number. Patients may also be rescreened at a later time if site closures or other logistical issues prevent randomization as planned. Patients presenting with a reduction in the IGA score between screening and baseline, with the IGA not qualifying as moderate or severe at the baseline visit (i.e., IGA score of 2, 1 or 0), will not be eligible for re-screening. For all rescreened subjects, the investigator/qualified site staff will record if the subject was rescreened on the rescreening eCRF and the original screening number the subject was issued prior to the current screening number.

Informed Consent for a rescreened subject must be obtained prior to performing any study-related assessment or collecting any data for the Screening Visit. For rescreening, all screening assessments must be performed as per protocol, except for the tuberculosis (TB) **work up**, if applicable, if performed not more than 12 weeks before randomization. However, the subject must repeat the QuantiFERON-TB Gold assay performed by the central laboratory.

### Information to be collected on screening failures

Subjects who sign an informed consent form and subsequently found to be ineligible prior to randomization will be considered a screen failure. The reason for screen failure should be recorded on the appropriate CRF. The demographic information, informed consent, and Inclusion/Exclusion pages must also be completed for screen failure subjects. No other data will be entered into the clinical database for subjects who are screen failures, unless the subject experienced a serious adverse event during the screening phase ([Section 10.1.3](#), SAE reporting). Adverse events that are not SAEs will be followed up by the investigator and collected only in the source data. If the subject fails to be randomized, the IRT must be notified within 2 days of the screen fail that the subject was not randomized.

## 8.2 Subject demographics/other baseline characteristics

Country-specific regulations should be considered for the collection of demographic and baseline characteristics in alignment with the CRF.

### 8.2.1 Demography

Subjects demographics data will include: age, gender, race and ethnicity.

### 8.2.2 Prior Lichen Planus medical history and previous therapies

The following information should be collected and entered in the relevant CRF page:

- lichen planus subtype: Cutaneous lichen planus, mucosal lichen planus, lichen planopilaris (note that the predominant subtype as well as potential concurrent subtypes, if present, are collected).
- date of first symptoms
- date of first diagnosis of lichen planus

- any treatments for lichen planus since initial diagnosis prior to study entry will be collected and recorded in the eCRF along with the duration of the prior therapy and reason for discontinuation.

### **8.2.3 Smoking history**

The current and/or previous tobacco use will be recorded prior to randomization, as well as the estimated number of pack-years based on the approximate consumption per year. Use of e-cigarettes will be recorded in the Medical history CRF.

### **8.2.4 Medical history/current medical conditions**

Relevant medical history and current medical conditions includes data prior to signing of the informed consent and should be recorded in the Medical History eCRF. Whenever possible, diagnoses and not symptoms should be recorded.

Significant findings that are observed after the subject has signed the ICF and that meet the definition of an AE must be recorded in the AE eCRF.

### **8.2.5 Prior and concomitant medications**

Concomitant medications and prior medications taken over the 6 months preceding study enrollment for reasons other than lichen planus will be captured at the screening visit, and updated as necessary in the relevant eCRF.

### **8.2.6 Determination of the tuberculosis status**

Determination of tuberculosis (TB) status should be done at Screening and should be performed as defined by local guidelines. The TB status must be determined by medical history, signs, symptoms, and TB testing (QuantiFERON-TB Gold assay). Any significant findings should be recorded in the eCRF ([Section 15.3](#)) for more details.

## **8.3 Efficacy**

The following section describes the efficacy measures applied in this study. Whenever possible the following assessments should be performed by the same evaluator throughout the study.

### **8.3.1 Investigator's Global Assessment (IGA)**

**The IGA grading should be done first**, before performing any other physician assessments (e.g. REU, LPPAI, etc). Whenever possible, the IGA assessment should be performed by the same evaluator throughout the study.

The IGA table ([Table 8-2](#)) will provide a harmonized, 5-point grading system to assess disease severity for patients of all 3 subtypes entering the study.

**The predominant subtype defines the IGA score of the patient.**

**The IGA grading is based on the predominant subtype alone**, meaning on the subtype of the cohort the patient is in. In addition, the IGA score is also collected **separately** for concomitant subtypes, if present.

**Table 8-2** Investigator's Global Assessment grading

IGA score	Cutaneous Lichen Planus	Mucosal Lichen Planus	Lichen Planopilaris
0 - Clear	No disease. Possible flat, hyperpigmented lesions.	No disease.	No active disease. Hypopigmented, cicatricial patches. Pull test negative.
1 - Minimal	Barely palpable (<0.5 mm), scattered papules, mild erythema. Typically associated with minimal pruritus.	Reticular, white, patch-type striations involving any oral or genital mucosal site(s) ("Wickham Striae"). Absence of ulcers. Typically associated with no symptoms.	Predominantly inactive disease (hypopigmented cicatricial patches). Absence of disease spreading. Pull test negative. Minimal scalp erythema and/or perifollicular erythema without scale. Typically associated with minimal pruritus.
2 - Mild	Moderately elevated papules (<1 mm) and/or small plaques (<2 cm  ). Involvement of limited areas, erythema. Typically associated with mild pruritus.	Plaque-type, mucosal lichen planus involving any oral or genital mucosal site(s). Absence of ulcers or presence of one focal ulceration (<0.5 cm  ). Typically associated with mild pain or sensitivity.	Rare perifollicular erythema, rare perifollicular hyperkeratosis and interfollicular scale. Stable or slowly spreading disease. Pull test negative. Typically associated with mild pruritus.
3 - Moderate	Thick, elevated (<2 mm), hypertrophic, violaceous papules or presence of non-hypertrophic, plaque-like disease (>2 cm  ), either generalized or involving specific areas or specific locations (e.g. face, neck). Red/violaceous erythema, possible scales. Typically associated with moderate pruritus.	Desquamative gingivitis or vulvitis. Presence of unilateral or bilateral ulcerations involving any oral or genital mucosal site(s). Overall area affected by ulceration should be <2 cm  . Typically associated with moderate pain and sensitivity.	Hairless patches with perifollicular and interfollicular erythema, follicular hyperkeratosis and interfollicular scaling. Active spreading disease. Pull test positive for telogen hairs. Typically associated with moderate pruritus, pain and/or burning.

4 - Severe	Generalized, papular or plaque-type, elevated lesions (>2 mm) OR localized hypertrophic lesions (>2 cm  ). Marked red/violaceous erythema. Possible scales, blisters and ulcers. Typically associated with severe pruritus.	Presence of bilateral or extensive unilateral ulcers involving any oral or genital mucosal site(s). Overall area affected by ulceration should be >2 cm  . Possible esophageal involvement (established by endoscopy). Typically associated with severe pain and sensitivity.	Hairless patches with perifollicular and interfollicular, intense erythema, extensive perifollicular and interfollicular scaling. Crusting, pustules. Active spreading disease. Pull test positive for telogen or anagen hairs. Typically associated with severe pruritus, pain and/or burning.
-------------------	--	--	--

**The grading should be mainly driven by the lesion characteristics.** Symptoms, such as pain or pruritus, may or may not be associated.

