## 2 Objectives and endpoints

**Table 2-1 Objectives and related endpoints**

Objective(s)	Endpoint(s)
Primary objective(s)	Endpoint(s) for primary objective(s)

 
To demonstrate the clinical efficacy of secukinumab 300 mg every 4 weeks (Q4W) in subjects with cutaneous lichen planus (CLP), mucosal lichen planus (MLP), or lichen planopilaris (LPP) inadequately controlled by topical therapies, with respect to improvement in Investigator's Global Assessment (IGA) score by Week 16, compared to placebo.
 
	
 
Achievement of IGA response at Week 16 Patients diagnosed with biopsy-proven forms of CLP, MLP or LPP will be considered responders if they achieve an absolute IGA score ≤2 at Week 16
 

Secondary objective(s)	Endpoint(s) for secondary objective(s)

 
The secondary objectives of this trial comprise the following: 
 
- evaluate the efficacy of secukinumab 300 mg Q4W compared to placebo throughout 16 weeks in Treatment Period 1;
 
- evaluate the long term efficacy of secukinumab 300 mg Q4W throughout 32 weeks in Treatment Period 2;
 
- evaluate the efficacy of secukinumab 300 mg Q2W in Treatment Period 2;
 
- evaluate the safety profile of secukinumab 300 mg throughout the duration of the study.
 
 
Detailed assessments are described the next section.
 
 
	
All subtypes Investigator's Global Assessment (IGA)	
 
Achievement of 2 points improvement in the IGA score from baseline to Week 16 and 32, and throughout the duration of the study Achievement of IGA 0/1 at Week 16 and 32, and throughout the duration of the study
 

Objective(s)	Endpoint(s)

• Dermatology Life Quality Index (DLQI)

	

• Absolute and relative change in DLQI from baseline to Week 16 and 32, and throughout the duration of the study

• Achievement of DLQI 0/1 score at Week 16 and 32, and throughout the duration of the study

• Patient assessment of itch (NRS)

	

• Absolute and relative change in NRS from baseline to Week 16 and 32, and throughout the duration of the study

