#### **Screening period:**

A screening period of up to 4 weeks is used to assess patient's eligibility for the trial and to washout/adjust prohibited medications. The screening period covers the time from the signature of informed consent/screening visit (-4 weeks) to the randomization visit (Week 0).

Patients can be re-screened if the patient fails the initial screening due to a transient condition (not related to LP) or due to an insufficient prohibited medication washout period. Subjects can be re-screened only once and no re-screening procedure should be performed prior to re-consenting the subject. Patients may also be rescreened at a later time if site closures or other logistical issues prevent randomization as planned. Patients presenting with a reduction in the IGA score between screening and baseline, with the IGA not qualifying as moderate or severe at the baseline visit (i.e., IGA score of 2, 1 or 0), will not be eligible for re-screening.

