**Table 8-3 LPPAI**

Symptoms	Score
Pruritus	0 - 3
Pain	0 - 3
Burning	0 - 3
Signs	
Scalp erythema	0 - 3
Perifollicular erythema	0 - 3
Perifollicular scale	0 - 3
Pull test	0 / 1 & anagen / total
Spreading	0 - 2

**Score for signs and symptoms:** 0=absent, 1=mild, 2=moderate, 3=severe

**Score for anagen pull test:** To conduct the anagen pull test grasp a small group of 10 - 20 hairs between the thumb, second and third finger at the scalp end of the hair shafts and pull away from the scalp with a slow, firm perpendicular force to slide the fingers to the ends of the hair. The result is recorded both as a binary value (**0** for **no** anagen hairs, **1** for the **presence** of anagen hairs) and as anagen hairs/total hairs pulled.

**Score for spreading:** 0 = no spreading, 1 = indeterminate, 2 = spreading. When the hair loss is difficult to judge, the issue of spreading is recorded as indeterminate.

The weights given to the symptoms (30%), signs (30%), anagen pull test (25%) and presence of spreading (15%) then lead to the final equation:

**LPPAI (0-10) = (pruritus + pain + burning + scalp erythema + perifollicular erythema + perifollicular scale)/3 + 2.5x(pull test) + 1.5x(spreading/2)**

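### In the mucosal cohort, one small ulcer fits both IGA grade 2 and grade 3, and that line decides both entry and primary response

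*Protocol*

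**What the plan says.** Protocol section 5.1 requires an IGA of at least 3 at screening and at baseline. Section 3 (Screening period) bars from re-screening a patient "with the IGA not qualifying as moderate or severe at the baseline visit (i.e., IGA score of 2, 1 or 0"). Protocol Table 2-1 says that patients "will be considered responders if they achieve an absolute IGA score ≤2 at Week 16". Protocol section 12.4.1 and SAP section 2.5.1 repeat this cut, and none of these places asks for a minimum change from baseline.

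Table 8-2 in Protocol section 8.3.1 defines the grades, and SAP Table 5-19 repeats it. The anchors on either side of the 2/3 line are:

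- **MLP.** Grade 2 is plaque-type disease with "Absence of ulcers or presence of one focal ulceration" below 0.5 cm². Grade 3 is desquamative gingivitis or vulvitis, and "Presence of unilateral or bilateral ulcerations involving any oral or genital mucosal site(s). Overall area affected by ulceration should be" below 2 cm².
- **Cutaneous (CLP).** Grade 2 is "Moderately elevated papules (<1 mm) and/or small plaques" below 2 cm², in limited areas. Grade 3 is "Thick, elevated (<2 mm), hypertrophic, violaceous papules or presence of non-hypertrophic, plaque-like disease" above 2 cm².
- **Scalp (LPP).** Grades 0 to 2 need a negative pull test. Grade 3 has "Pull test positive for telogen hairs".

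The only guidance on a doubtful grade is that lesion characteristics count for more than symptoms. The same evaluator is to be used where possible. Section 8.3.5 describes the scale as newly developed for this trial.

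**The concern.** A one-grade difference in reading turns a grade 3 entrant into a responder. If the written anchors allow both grades for the same lesion, a response can be recorded without any change in disease.

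The entry rule makes this one-directional. A patient in the overlap is enrolled only if read as 3, so a later re-reading of the same lesion can only move towards response. Both arms gain such responders, but the arm with more non-improved patients gains more. The placebo rate rises further and the difference shrinks.

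IGA response at Week 16 is the only endpoint in the proof-of-concept (PoC) rule, which is applied to each cohort of 24 versus 12 patients. Sites could also settle the same presentation in opposite ways.

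**Working it through.** **1. Does one lesion meet both MLP grades?** Take plaque-type mucosal disease with a single ulcer of 0.3 cm².
- Grade 2 allows one focal ulcer below 0.5 cm². 0.3 < 0.5, so it is met.
- Grade 3 allows unilateral ulceration with overall area below 2 cm². 0.3 < 2 and there is no lower limit, so it is met.
- The lesions-over-symptoms rule does not help, because both descriptors are lesion characteristics.

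**2. The other two columns.**
- CLP: the papule heights in grades 2 and 3 are upper limits only (below 1 mm, below 2 mm). Generalised, non-hypertrophic papules of 0.5 to 2 mm fit no grade: grade 1 needs less than 0.5 mm, grade 2 limited areas, grade 3 hypertrophic papules or plaque-like disease above 2 cm², and grade 4 generalised disease above 2 mm. This is a gap.
- LPP: Table 8-2 does not define a positive pull test. It calls the test positive on telogen hairs at grade 3. The only procedure described, in section 8.3.4, scores 1 for the presence "of anagen hairs) and as anagen hairs/total hairs pulled". This is an undefined term.

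**3. Reproducing the plan's figure.** Inputs from Protocol sections 12.4.2 and 12.8:
- n = 24 and 12, response rates 50% and 20%, and a Beta(1/3, 1/3) prior in each arm.
- The posterior in each arm is Beta(1/3 + s, 1/3 + n − s), where s is the number of responders.
- PoC is declared if Pr(δ > 0) > 0.90 and Pr(δ > 0.15) > 0.50.

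Summing the binomial probabilities over all outcomes that meet both criteria gives 0.712, as in Table 12-1. All 30 cells of that table reproduce to three decimals.

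The rule is sensitive to single placebo patients. With 2 placebo responders of 12, PoC needs at least 9 secukinumab responders of 24. With 3 it needs 12.

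**4. Sensitivity (assumed; the documents give no such rate).** Let a share f of the cohort lie in the overlap, and let half of those not truly improved be read as grade 2. The graded rate is then p′ = p + (1 − p) × f/2. For f = 10%, secukinumab is 0.50 + 0.50 × 0.05 = 0.525 and placebo is 0.20 + 0.80 × 0.05 = 0.24.

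| f | Secukinumab | Placebo | Difference | PoC probability |
|---|---|---|---|---|
| 0 | 0.500 | 0.200 | 0.300 | 0.712 |
| 2% | 0.505 | 0.208 | 0.297 | 0.701 |
| 5% | 0.5125 | 0.220 | 0.2925 | 0.686 |
| 10% | 0.525 | 0.240 | 0.285 | 0.661 |
| 20% | 0.550 | 0.280 | 0.270 | 0.614 |
| 30% | 0.575 | 0.320 | 0.255 | 0.573 |

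With no true effect and 20% in both arms, the false-PoC probability per cohort is 0.087. At f = 20% (28% in both arms) it is 0.109.

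**The case against.** Several safeguards limit the effect. A borderline patient must be read as 3 at both screening and baseline. The same evaluator is used where possible. Assessors are blinded, so misgrading should be similar in both arms, and the false-PoC probability rises by only about 2 points. All this stands. It makes the problem mainly one of dilution, but it does not tell a rater which grade a single small ulcer receives.

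Grade 3 uses the plural for ulcers, which could be read as more than one. That is possible, but the same phrase admits unilateral ulceration and sets no minimum number or area.

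The size is assumed. In addition, the planned 20% may be a placebo rate as graded, in which case adding misgrading counts part of it twice. This stands, and it is a reason to read the table as a range and not as a forecast.

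A reader might infer that all three columns let unchanged disease move from 3 to 2. The documents do not support that:
- In CLP, the words thick and hypertrophic partly separate the grades, and the failing case has no grade at all.
- In LPP, section 8.3.4 scores an anagen component of a different instrument and never calls a telogen-only pull negative. Total hairs pulled are recorded as well, so non-anagen hairs may be obtainable by subtraction.
- In MLP, desquamative gingivitis without ulcers does not fall into grade 2. There, absence of ulcers only qualifies plaque-type disease, while grade 3 names gingivitis.

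A reader might also apply a symmetric error rate to every patient, which gives lower PoC probabilities. That model misgrades patients far from the line and does not describe this overlap.

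**Conclusion.** The point holds for the MLP cohort. As written, a single ulcer below 0.5 cm² meets grades 2 and 3, and the plan can count unchanged disease as a primary response. The CLP gap and the undefined pull test are lesser defects at the same line. They leave the grade to the rater but do not by themselves show a change from 3 to 2.

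Under the assumptions in the table (planned rates of 50% and 20%, an overlap share of 2% to 30%, half of the non-improved read as grade 2, equal in both arms), PoC probability in the affected cohort falls from 0.71 to between 0.70 and 0.57. At the low end this is negligible. At the high end it is about 14 points (0.712 − 0.573 = 0.139). The documents do not show where in that range the trial lies.

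The sample-size figure is correct on its own inputs. The secondary IGA 0/1 endpoint does not use this line. The endpoint of at least 2 points improvement uses it only for patients who enter at grade 4.

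**What to change.** Edit Protocol Table 8-2 and SAP Table 5-19 together so that grades 2 and 3 are mutually exclusive:

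- **MLP:** word grade 3 so that it excludes the single focal ulcer below 0.5 cm² already assigned to grade 2. This uses only the table's existing limits.
- **CLP:** have the sponsor assign a grade to generalised, non-hypertrophic papules of 0.5 to 2 mm.
- **LPP:** have the sponsor state which hairs make the IGA pull test positive, and reconcile that with section 8.3.4.
- Apply the same wording at screening, baseline and Week 16.

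A general rule to assign the higher grade in any doubt is not advised. It would also move the IGA 0/1 line, which decides whether a placebo patient enters Treatment Period 2 (Protocol sections 3 and 9.1.1).

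The cost is a short amendment and a note to raters. Patients already graded on the current table must be flagged, because a mid-trial change puts two versions of the scale inside a small cohort. An MLP patient whose only grade 3 feature is one ulcer below 0.5 cm² would no longer meet the entry grade.

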### 8.3.2 Physician's assessment of surface area of disease (PSAD)

The Physician Assessment of Surface Area of Disease (PSAD) evaluates the extent of cutaneous lesions. Since no validated scales are available to quantify the area of disease in CLP, the present study will utilize the PSAD grading score as previously reported in the only randomized trial conducted with a biologic therapy in CLP (etanercept, NCT00285779).

The PSAD will be estimated by the investigator/trained qualified designee from the percentages of areas affected, including head, trunk, upper limbs and lower limbs. Whenever possible, the same assessor should perform the PSAD assessment at all visits. The assessor will report the percentage of the surface area involved with disease using a Likert scale.

Assessment scores range from 0-5, with lower scores corresponding to lower percentages of surface area with disease.

**0:** clear

**1:** <2% of the total body surface area. Small, localized papules

**2:** 2-9% of the total body surface area. Lesions affecting limited areas (e.g. wrists or ankles)

**3:** 10-29% of the total body surface area. Lesions affecting extensive areas (e.g. upper limbs or back)

**4:** 30-50% of the total body surface area. Lesions affecting extensive areas or in multiple locations (e.g. trunk and lower/upper limbs)

**5:** >50% of the total body surface area. Generalized involvement

*As reference, the percentages utilized for the Body Surface Area (BSA) assessment should be considered (head=10%, trunk=30%, upper limbs=20%, lower limbs=40%).*

**Post-inflammatory hyperpigmentation should NOT be considered as surface area affected by the disease.**

The PSAD assessment is required for all subjects enrolled in the CLP cohort. In addition, the PSAD assessment is required for subjects enrolled in the MLP cohort in case they have a **concomitant** cutaneous involvement.

### **8.3.3 Reticulations, erythema and ulcerations (REU) score**

The reticulation, erythema and ulcerations score (REU score) was developed by Piboonniyom et al. as a semiquantitative scale for the assessment and monitoring of oral lichen planus as well as oral graft-versus-host disease ([Piboonniyom et al 2005](#)). It measures disease severity based on 3 dimensions: reticulation, erythema and ulceration. Whenever possible, the REU assessment should be performed by the same evaluator throughout the study.

The REU score is applied for all patients in the MLP cohort who have an **oral** presentation of the disease. In addition, the REU scoring is also done for patients in the CLP cohort in case they have a concomitant **oral** involvement.

The assessment is done as follows:

The oral cavity is divided into the following 10 sites:

- upper/lower labial mucosa
- right buccal mucosa
- left buccal mucosa
- dorsal tongue
- ventral tongue
- floor of mouth
- hard palate mucosa
- soft palate/tonsillar pillars
- maxillary gingiva
- mandibular gingiva

The severity of the lesions is scored for each site individually according to the presence of reticular/hyperkeratotic, erosive/erythematous and ulcerative lesions:

- **Reticulation:** reticular/hyperkeratotic lesions: 0 - 1
  - 0: no white striations
  - 1: presence of white striations or keratotic papules
- **Erythema:** erosive/erythematous lesions by area of involvement: 0 - 3
  - 0: no lesion
  - 1: lesions  $< 1 \text{ cm}^2$
  - 2: lesions 1 - 3  $\text{cm}^2$
  - 3: lesions  $> 3 \text{ cm}^2$
- **Ulceration:** ulcerative lesions by area of involvement: 0-3
  - 0: no lesion
  - 1: lesions  $< 1 \text{ cm}^2$
  - 2: lesions 1 - 3  $\text{cm}^2$

- 3: lesions > 3 cm^2

For each of the 3 clinical dimensions, a score is then derived by summation of the scores from all 10 oral cavity sites: Reticular score =  $\sum R$ , erythema score =  $\sum E$ , and ulcerative score =  $\sum U$ .

These 3 scores then add up to a **total weighted score**:  $\sum R + \sum(E \times 1.5) + \sum(U \times 2.0)$ .

